Research Design. This study will evaluate the feasibility and usability of assessing real-time residential environmental exposures (VOCs/PM_{2.5}), asthma symptoms, and lung function using an innovative combination of commercially available technology (Aim 1).⁶⁰ In addition, we will use observational design to explore the unintended effects of these residential environmental exposures on adults with poorly controlled asthma in the era of COVID-19 (Aims 2 & 3).

Sample. Eligibility criteria include GCAS participants who: (1) indicated willingness to be contacted for future research, (2) reported high use of disinfectant/cleaning products since COVID-19 (≥ 5 per week), and current ACT ≤ 19 . Non-US residents and non-English speakers will be excluded. We will strive to have at least 20% of the sample representing minority populations. Fifty individuals meeting these criteria will be randomly selected and invited to participate in this study using their preferred contact method (94% indicated email). Interested individuals will be directed to a REDCap survey link to confirm willingness to participate, verify eligibility, and provide current contact information. We will randomly select replacements if no response is received after 2 contact attempts over two weeks or lack of interest is indicated.

Data collection methods. Three innovative data collection methods will be integrated in this feasibility study: Ecological Momentary Assessment (EMA) downloaded to participants' smartphone, Awair Omni Indoor Air Quality Monitor®, and Zephyr_x Spirometer.

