Zephyr_x Spirometer⁷² system allows for laboratory quality pulmonary function tests (PFTs) at home (FVS-forced vital capacity, FEV₁-forced expiratory volume in 1 second, FEV₁/FVC, flow-volume loop). The system consists of an FDA approved handheld Bluetooth spirometer (MIR Spirobank Smart), and a mobile application that works on a smartphone or tablet device. The MIR Spirobank bank measures 49x109x21 mm and weighs 60.7 g. Participants share PFT results through their app and researcher team members will access a HIPAA compliant portal to view participants' PFT results in real time. An in-App video coaching feature guides the participant through the PFT maneuver. Each maneuver conducted by the participant creates a time and date stamped American Thoracic Society standard PFT report accessible through the portal. Data will be exported from the dashboard to a .CSV file.

Procedures (Figure 3)

1. Randomly selected individuals from the CGAS study who meet eligibility criteria will be invited to participate in the current study. Those interested will be directed to a REDCap link to complete an E-consent form and baseline questionnaire.
2. An Awair Indoor Air Quality Monitor and a Zephyr_x Spirometer will be mailed to each participant along with a quick start guide, written instructions with a link to an instructional video, and research team contact information. Once received, a research team member will conduct a live chat with each participant to enable the devices, download apps (EMA, Zephyr_x), setup and test the devices and apps, review the protocol, and address questions. Participants will be instructed to place the portable Awair air quality monitor in the room where they spend the most time during the day and at night where they sleep.
3. A 3-day run-in period will be completed during which the participants will become familiar with the devices and troubleshoot issues (Awair requires 24-48 hours to calibrate VOC sensors). Study personnel will be available to answer questions/address technical issues. After the run-in period, a research team member will contact the participant to launch the 14-day data collection period.

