- *EMA survey triggered by VOCs/PM_{2.5} greater than optimal range as detected by the Awair* will query asthma symptoms, lists of probable sources of elevated VOCs or PM_{2.5}.
- *EMA survey 30-minutes after Awair air quality notification* queries mitigation strategies used (from lists) and asthma symptoms.
- *Home spirometer use* (Yes:No) queried in each EMA survey

Home spirometer. FEV₁% predicted– a standard metric of lung function for those with asthma.

Seven-Day check-in. Open-ended questions to identify any trouble-shooting areas, determine if adjustments need to be made, and assess ease of use of the app/devices. Interactions will be recorded and reviewed by the research team for patterns and to identify any adjustments that are needed.

Participant feasibility assessment. At the end of the 14-day data collection period, participants will be asked to respond to a short REDCap survey assessing acceptability, appropriateness, and feasibility of the indoor air quality monitor, EMA notifications, and the home spirometer with response ranging from 1=completely disagree to 5=completely agree. A random sample of 20 participants will be interviewed to further explore these factors using open-ended questions such as "Tell us what you liked/didn't like about the indoor air quality monitor", "Describe the strengths/concerns about the survey you received about your home indoor air quality".

Data Analysis

Each day of observation will be divided into four 4-hour periods between 6 a.m. and 10 p.m. Data from a given period will be considered as follows:

1. Period specific data from all event-contingent EMA prompts [prompts triggered by high indoor air VOC/PM_{2.5} readings] will be analyzed. If multiple event-contingent prompts were answered, data will be averaged across all event-contingent prompts during that period.
2. Data from all answered baseline and random [signal-contingent] EMA prompts will be considered.

Aim 1. For this aim, we will assess:

1. Compliance with the EMA prompts as indicated by the frequency of responses to prompts, specifically:
 - a. # of responses (complete:incomplete)/number of prompts
 - b. # times spirometer used/number of prompts
 - c. # times environment modified/number of event-contingent prompts
2. Compliance as described in 1a-1c by 4-hr each period.

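### Aim 1 compliance has an undefined prompt denominator and no retention measure, and acceptability is rated only at day 14, so feasibility could be overstated if people stop early

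*Combined protocol and SAP*

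**What the plan says.** Data Analysis, Aim 1, sets three compliance ratios, to be given overall and by 4-hour period:

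- 1a, number "of responses (complete:incomplete)/number of prompts"
- 1b, number of "times spirometer used/number of prompts"
- 1c, number of "times environment modified/number of event-contingent prompts"

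The text does not define a prompt for 1a and 1b as planned, sent or delivered. It does not say whether sending ends when a person stops, or whether ratios are pooled or calculated per participant. Aim 1 also covers how long each participant uses the air monitor.

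Procedures, steps 4 to 6, give one morning survey and two random surveys a day. Alert surveys follow a notification from the monitor, with a second survey 30 minutes later.

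On acceptability, the section on participant feasibility assessment says: "At the end of the 14-day data collection period, participants will be asked to respond to a short REDCap survey". Ratings run from 1 to 5 and are analysed descriptively, with no stated denominator. Twenty randomly chosen participants are interviewed at the same stage. Before that, under Procedures step 7, staff contact anyone with a 24-hour data gap, partly to establish acceptability, and check in with each participant at about day 7.

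On participant flow, the Sample section says: "Fifty individuals meeting these criteria will be randomly selected and invited to participate in this study". Replacement is described only at invitation: "We will randomly select replacements if no response is received after 2 contact attempts over two weeks or lack of interest is indicated". A run-in follows ("A 3-day run-in period will be completed during which the participants will become familiar with the devices and troubleshoot issues"), after which "a research team member will contact the participant to launch the 14-day data collection period". No retention or completion rate is planned, and no rule covers people who stop.

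**The concern.** Feasibility and usability are Aim 1, and the findings are meant to support a powered study. A compliance ratio answers that question only if the reader knows whose prompts, over what time, are in the denominator. If a participant removes the app and prompting ends, the remaining days add neither responses nor non-responses. The ratio then describes time under active participation, not the 14 days the participant agreed to.

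Alert prompts raise the same issue more directly, because they exist only while the monitor is working. Mixing them into 1a and 1b also lets homes with many alerts dominate if the ratio is pooled.

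The rated survey has a parallel weakness. Someone who stops on day 4 may never give a rating, and people who found the protocol unacceptable are plausibly the ones who stop. Both results could therefore look better than the experience of everyone who began.

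**Working it through.** **Nothing to reproduce.** The plan gives no compliance target, expected response rate, dropout rate or sample-size calculation. The response and stopping rates below are assumptions.

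**Planned scheduled prompts.** From Procedures step 4: (1 morning + 2 random) × 14 days = 42 per participant. With an assumed 50 starters, 50 × 42 = 2,100. The account of the Chicago Asthma Consortium meeting says routine notifications were cut from 3 to 2 a day. If that means two in total, the count is 2 × 14 = 28. The daily count cancels in the ratios below, so the sizes do not depend on it.

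**Formulas.** Let r be the response rate while active, d the share who stop, and s the last active day.

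- Prompts cease at stopping: compliance = r.
- Prompts continue, or the denominator is all planned prompts: compliance = r × [(1 − d) + d × s/14].
- Gap = r × d × (1 − s/14).

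**Worked case, r = 0.80, d = 0.20, s = 7.** Of 50 starters, 40 receive 42 prompts and 10 receive 21 before stopping: 1,680 + 210 = 1,890. Responses are 0.80 × 1,890 = 1,512.

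- Prompts cease: 1,512/1,890 = 0.80.
- All planned prompts: 1,512/2,100 = 0.72.
- Gap: 8 points. If prompts keep being sent, both calculations give 0.72 and the gap is 0.

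**Range (r 0.60 to 0.90, d 10% to 30%, s 3 to 10), if prompts cease.**

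- Smallest gap: 0.60 × 0.10 × (1 − 10/14) = 0.017.
- Largest gap: 0.90 × 0.30 × (1 − 3/14) = 0.212.

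**If stoppers also respond less before stopping** (assumed 60%, against 80% in those who continue; prompts cease):

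| Stop | Over prompts while active | Over all planned |
|---|---|---|
| 10% after day 4 | 10.32/13 = 79.4% | 10.32/14 = 73.7% |
| 20% after day 4 | 9.44/12 = 78.7% | 9.44/14 = 67.4% |
| 30% after day 7 | 9.10/11.9 = 76.5% | 9.10/14 = 65.0% |

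The 20% row, for example, is 0.8 × 14 × 0.8 + 0.2 × 4 × 0.6 = 9.44 responses per planned daily prompt.

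**Alert prompts.** The monitor runs from the mains with an 8-hour battery back-up. Left unplugged beyond that, it sends no notifications. Its alert prompts then drop out of 1c entirely and out of 1a and 1b in part. This follows from the design, whatever the app does. On weighting, a home with an assumed 5 alerts a day gets 3 + 5 × 2 = 13 prompts, against 3 in a home with none. In a pooled ratio it would carry 13/3 = 4.3 times the weight.

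**Acceptability.** Assume 85% of completers are favourable, 0% to 40% of stoppers are, and no stopper is surveyed. The reported figure is 85%. Over everyone who started, 0.85 × (1 − d) + q × d, with q the share of stoppers who are favourable, gives:

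- d = 10%: 76.5% to 80.5%
- d = 20%: 68% to 76%
- d = 30%: 59.5% to 71.5%

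**The case against.** A reader might infer that the plan counts only prompts issued, asks about acceptability only at day 14, loses early stoppers from both measures, and so overstates feasibility. The documents do not support that reading:

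- The plan never says that only issued prompts count, and never says that sending ends when someone stops. A silent participant who is still sent prompts adds to the denominator and not the numerator, which lowers compliance.
- Acceptability is also probed when data lapse for 24 hours, which reaches the people most likely to be stopping. Ease of use is covered at about day 7, and those contacts are recorded and reviewed.
- Prompts before stopping still count. Monitor duration is assessed for each participant and can reveal early stopping. The survey is not stated to be limited to completers.
- Pooling is not stated either. The plan to compare use and acceptance across participant characteristics suggests participant-level summaries.
- Counting undelivered prompts as unanswered would record an interface failure as participant non-compliance.
- No progression threshold depends on the ratio.

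All of this stands, and it limits the point without removing it. The denominator is still undefined. Monitor duration does not show withdrawal from the surveys or spirometry. The gap contacts and day-7 check-in use no rating scale and have no Aim 1 analysis beyond team review. No provision is made to survey people who stop.

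**Conclusion.** The point holds as a gap in definition and reporting that leaves room for bias; it is not a demonstrated overstatement. Two analysts following the same text could report compliance for scheduled prompts that differs by 0 to about 20 points. The gap is 0 if prompts continue after stopping. It is 1.7 to 21.2 points if they cease, under the assumed response rates, stopping shares and stopping days. For alert prompts, loss of the denominator when the monitor is off is built into the design, but the documents give no alert frequency from which to size it. The shortfall in rated acceptability depends wholly on how many stop, how they would have rated the protocol, and whether they are surveyed.

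Losses during the 3-day run-in come before the 14-day prompts, so no prompt ratio would show them. Feasibility is the leading aim and the remedy is cheap, so this should be settled before results are seen.

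**What to change.** 1. For scheduled prompts, report completion per participant over all planned prompts, for everyone launched into the 14 days. That is 42 by the Procedures; confirm it against the account of the Chicago Asthma Consortium meeting.
2. Beside it, show response to delivered prompts, with technical non-delivery counted separately from non-response.
3. Report alert-prompt compliance separately, and summarise per-participant ratios instead of one pooled figure. No fixed number of alerts is planned, so read this result next to the monitor duration already being collected.
4. Report participant flow from consent through run-in and launch to day 14.
5. Offer the rated survey when a participant stops, and report its response rate out of everyone launched.

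The first four items change analysis and reporting wording, given that prompt delivery is logged. The fifth needs one earlier survey link. The downside is a compliance figure that may look less favourable.

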Presenting to a healthcare facility with symptoms of wheezing and shortness of breath can initially complicate diagnosis and treatment for asthma exacerbation or COVID-19.⁴ Currently, the available case study evidence is unclear whether those with asthma are at greater risk or overrepresented among cases with severe COVID-19 outcomes.¹⁴⁻¹⁷ Recent US data has shown higher rates of asthma in hospitalized COVID-19 patients compared to COVID-19 patients in the ambulatory setting.¹⁸ Further, in one US cohort study, asthma was the second most common co-morbidity after obesity among those 18-49 years old with COVID-19.¹⁹ It is also unclear if individuals with asthma are overrepresented among those currently seeking testing for COVID-19 across the nation. While cardiovascular disease, kidney disease, and diabetes have been associated with greater COVID-19, mortality²⁰ pulmonary conditions such as asthma, which is exacerbated by respiratory viruses, have not been well studied in COVID-19.

Residential asthma triggers. Adults ordinarily spend about 15 hours/day indoors^{11,12} and since COVID-19, those hours have largely been spent in their homes. Environmental asthma triggers in residential settings include dust mites, animal dander, mold, moisture, tobacco smoke, particulates, cockroach allergen, mouse/rat allergens, VOCs, and nitrogen dioxide.^{13,21,22} Indoor residential air quality has been associated with decreased general health, asthma symptoms, airway inflammation, asthma exacerbations and decreased lung function in adults with asthma.²³⁻²⁶ We will focus on residential VOCs, specifically disinfectants/cleaners, and particulates as potential asthma environmental triggers exposures increased during the COVID-19 pandemic.

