4. During the 14-day data collection period, data from the EMA will be collected using EMA software platform on a personal smartphone (iOS or Android) and EMA software platform.⁷³ Each morning, participants will receive an EMA survey concerning asthma symptoms and a reminder to use their spirometer. Additionally, EMA surveys addressing disinfectant use, asthma symptoms, and spirometry will occur randomly twice/day (6am – 10pm) or tailored for those working off hours (Appendix).
5. A custom interface between the EMA platform and the Awair indoor air quality monitor will alert participants when levels of indoor VOCs or particulates are detected outside the optimal range (Table 1). The air quality monitor will communicate with the EMA platform using publicly available application programming interface (api). Upon notification from the Awair, the EMA will signal the participant to complete a brief survey on disinfectant use/air particulate exposure (depending on the alert), current asthma symptoms, and proximity to the Awair (Appendix). The EMA will then direct participants to use the spirometer. Participants experiencing symptoms will be guided to follow their asthma action plan/provider instructions.
6. Thirty minutes after VOC/PM_{2.5} notification, a second EMA notification will be sent for participants to complete a survey on mitigation strategies, respiratory outcomes, and spirometry use if not already completed (Figure 4).
7. Research personnel will monitor use of these devices/apps and contact participants if a 24-hour gap in data is noted to address concerns and determine acceptability. Research team members will check-in with each participant at about the 7-day mark to address technical concerns and ease of use.

8. At the end of the 14 days, participants will complete a short acceptability, appropriateness, and feasibility REDCap survey. A random sample of 20 participants will be interviewed to provide further insights.
9. Participants will be asked to return the Awair in the provided mailer. The Awair will be fully disinfected per manufacturer's directions. Participants will keep the Zephyr_x spirometer as an incentive.

Baseline Measures

The following measures will be administered at baseline via REDCap:

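### Aim 1 ratios 1b and 1c count prompts received away from home, so they mix being unable to act with not complying, most clearly for 1c

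*Combined protocol and SAP*

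**What the plan says.** Data Analysis, Aim 1, lists three compliance ratios. Item 1b is "times spirometer used/number of prompts" and item 1c is "times environment modified/number of event-contingent prompts". Item 2 repeats them by 4-hour period, and the text that follows plans to compare use and acceptance by participant characteristics such as age, health and education. None of these ratios has a rule about where the participant was when the prompt arrived.

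Procedures, step 4, runs the surveys on the participant's own phone. The schedule is a morning survey ("Each morning, participants will receive an EMA survey concerning asthma symptoms and a reminder to use their spirometer") plus surveys that "will occur randomly twice/day (6am – 10pm) or tailored for those working off hours". The tailoring is by working hours, not by location. In step 5 an interface to the air monitor "will alert participants when levels of indoor VOCs or particulates are detected outside the optimal range". The resulting survey asks about the exposure, "current asthma symptoms, and proximity to the Awair". No stated analysis uses the proximity answer.

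Procedures, step 2, has the participant keep the monitor in the main daytime room and, at night, where they sleep. The data collection section describes the spirometer as a handheld Bluetooth device of 60.7 g that works with a smartphone or tablet. Elsewhere the plan calls it a home spirometer. It does not say whether the device should be carried.

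**The concern.** A phone prompt follows the person, while the monitor stays in the home. Other occupants or outdoor air can push a reading out of range while the participant is at work or on an errand. That alert still enters the denominator of 1c, although the participant is in no position to open a window or stop the source. A random prompt received away enters the denominator of 1b in the same way.

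The reported ratio then combines two things: how often the participant was where they could act, and how often they acted when they could. Aim 1 is about the second, and its results are meant to inform a later powered study. The comparisons by characteristics and by 4-hour period are exposed too, since age, health, employment and time of day all bear on who is at home.

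**Working it through.** The plan gives no expected compliance rate, target or sample-size calculation, so there is no stated figure to reproduce. The check is arithmetic on the denominators.

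**Inputs**
- Scheduled prompts (Procedures, step 4, over 14 days): 1 morning + 2 random = 3 per day; 3 × 14 = 42 per participant, of which 2 × 14 = 28 are random.
- Number of alert prompts: not given.
- Share of prompts received away from home, *a*: not given, so assumed at 0, 0.10, 0.25 and 0.50. It need not be the same for random and alert prompts. Alerts set off by the participant's own cleaning or cooking arrive while they are at home, which would lower *a* for alerts.

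**Formulas**
- 1c ceiling = 1 − *a*. This assumes that only the participant's own action counts and that it must be possible at the time of the alert.
- 1b ceiling over scheduled prompts, spirometer never carried = (1 + 2(1 − *a*))/3 = 1 − 2*a*/3. This assumes that morning prompts arrive at home and that a use counts only at its prompt.
- 1b ceiling if the spirometer is carried on half of the away occasions = 1 − *a*/3, other assumptions unchanged.

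| *a* (assumed) | 1c ceiling | 1b ceiling, never carried | 1b ceiling, carried half the time |
|---|---|---|---|
| 0 | 100% | 100% | 100% |
| 0.10 | 90% | 93.3% | 96.7% |
| 0.25 | 75% | 83.3% | 91.7% |
| 0.50 | 50% | 66.7% | 83.3% |

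For example, at *a* = 0.25 with the device never carried: 14 + 28 × 0.75 = 35 prompts can be acted on, and 35/42 = 83.3%.

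**Effect on a comparison.** Take two groups that both act on 80% of the prompts they receive at home (assumed). One is never away, and the other is away for half of the prompts (for 1b, half of the random ones, with the spirometer left at home). On 1c they would show 80% and 0.80 × 0.50 = 40%. On 1b over scheduled prompts they would show 80% and 0.80 × 0.667 = 53.3%. Behaviour at home is identical, so the whole gap is presence.

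**The case against.** A reader might infer that every prompt received away is scored as a failure, and that a fully willing participant cannot reach 100%. For 1b the documents do not support that. The spirometer is pocket-sized and phone-linked, and nothing tells participants to leave it at home. Item 1b is a count of uses over a count of prompts with no linking window, so a use after returning home could enter the numerator. For 1c, the plan does not say who must modify the environment.

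A reader might also take a size from the Significance section: "Adults ordinarily spend about 15 hours/day indoors". With 8 of those hours overnight, 7 of the 16 prompt hours would be at home and 9/16 = 56% of random prompts would arrive away. That figure is for ordinary times, however, and counts time indoors, not time at home. The same sentence adds that since COVID-19 those hours have mostly been at home. It cannot fix *a*, and the loss may be small: at *a* = 0.10 the 1b ceiling is still 93.3%.

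Other points stand in part. The all-prompt ratio is a legitimate quantity, namely what a prompt yields in daily life. The 4-hour breakdown would show daytime dips, and the 24-hour-gap contacts, the day-7 check-in, the exit survey and the 20 interviews can pick up reasons for non-use. None of these separates absence from non-compliance prompt by prompt. The survey content is in an Appendix that is not in the available text, so a location item in the morning or random surveys cannot be ruled out.

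**Conclusion.** The point holds, most firmly for 1c. Both denominators count prompts regardless of where the participant is, and the proximity answer that could partly separate the cases is collected at alerts but not used. For assumed away shares of 0.10, 0.25 and 0.50, the 1c ceiling is 90%, 75% and 50%.

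For 1b the effect is conditional. The corresponding ceilings of 93%, 83% and 67% require that the spirometer is never carried, that uses are tied to prompts and that morning prompts arrive at home. They rise if the device is sometimes carried or if later uses count.

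A reader might go further and infer a wrong feasibility decision. The documents do not support that, because they set no compliance threshold or go/no-go rule. The harm is a descriptive rate biased downward as a measure of willingness or ability to use the devices, and comparisons by participant characteristics and by 4-hour period that could reflect who is at home.

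**What to change.** - Keep the all-prompt versions of 1b and 1c.
- Beside them, use the proximity item to report 1c, and 1b for alert prompts, among answered prompts where the participant was at home or near the monitor.
- If the Appendix does not already have one, add a one-tap at-home item to the morning and random surveys, so that 1b can be split in the same way for scheduled prompts.
- State how a spirometer use is credited to a prompt, and whose action counts as modifying the environment.
- Show the comparisons by participant characteristics on both ratios. The at-home ratio alone conditions on having answered the prompt.

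The cost is a few lines of analysis text and at most one extra tap in two short surveys. The limits should be stated with the results: location is unknown for unanswered prompts, so the at-home ratio describes responders only, and proximity to the monitor is an imperfect proxy for being at home.

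### Aim 1 item 1c is labelled compliance, but as written it is follow-up response multiplied by mitigation behaviour and cannot separate the two

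*Combined protocol and SAP*

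**What the plan says.** Data Analysis, Aim 1, item 1 introduces three ratios under the description "Compliance with the EMA prompts as indicated by the frequency of responses to prompts". Item 1a is the number "of responses (complete:incomplete)/number of prompts". Item 1b puts spirometer uses over prompts. Item 1c is the number of "times environment modified/number of event-contingent prompts". Item 2 repeats all three by 4-hour period. The opening of Data Analysis defines event-contingent prompts as those set off by high VOC or PM2.5 readings.

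Procedures, step 5 describes what follows an alert. The participant is asked for a brief survey, and then "The EMA will then direct participants to use the spirometer". Those with symptoms are pointed to their own action plan or provider's instructions. Under step 6, half an hour after the alert, "a second EMA notification will be sent for participants to complete a survey on mitigation strategies". The section on EMA survey items adds that this later survey asks which mitigation strategies were used, chosen from lists.

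The plan does not say how an unanswered 30-minute survey enters 1c. It does not define a modified environment further, and it sets no expected value or threshold for 1c.

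**The concern.** There are two separate problems.

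**Numerator and denominator come from different prompts.** Modification becomes known only if the 30-minute survey is answered, but each alert counts in the denominator whether or not it was. The ratio therefore falls when people skip the follow-up and also when they answer it and report no change. A reader of the result cannot tell which happened.

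**The label does not fit.** Items 1a and 1b count things that the prompts request. Item 1c counts an action that the visible steps ask participants to report, not to carry out. A low value may mean that there was nothing to change, that the participant chose not to change it, or that the follow-up was missed. Only the last is plainly a failure to comply with a prompt.

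At stake is a clear reading of Aim 1: whether participants answer the follow-up survey, and how often an alert is followed by mitigation. As defined, 1c answers neither question.

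**Working it through.** The plan states no figure for 1c, so there is nothing to reproduce. The check is on the formula.

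**Inputs.** From the documents: the 1c ratio, the definition of an event-contingent prompt, and the 30-minute survey as the only described source of the numerator. Assumed for illustration: A alerts, follow-up response rate f, mitigation rate m among answered follow-ups, and at most one modification counted per alert.

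**Does the denominator mean prompts sent?** Item 1a has responses in its numerator, so its prompts must be prompts sent. Where the plan restricts itself to answered prompts it says so, as in the averaging rule: "If multiple event-contingent prompts were answered, data will be averaged across all event-contingent prompts during that period". Item 1c carries no such restriction. The literal reading is therefore all alert-triggered prompts. This is an inference from the formula, not a written rule.

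**Formula.** Reported modifications = A × f × m, so

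1c = (A × f × m) / A = f × m.

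**Results with m = 50%:**

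| Follow-ups answered (f) | 1c as written (f × m) | Mitigation among answered follow-ups |
|---|---|---|
| 100% | 1.00 × 0.50 = 50% | 50% |
| 90% | 0.90 × 0.50 = 45% | 50% |
| 70% | 0.70 × 0.50 = 35% | 50% |
| 60% | 0.60 × 0.50 = 30% | 50% |

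**The two components cannot be recovered from 1c.** Answering 100% and modifying after 40% gives 1.00 × 0.40 = 40%. Answering 40% and modifying after 100% gives 0.40 × 1.00 = 40%.

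**What 1c does bound.** If none of the unanswered alerts was mitigated, the true per-alert rate is f × m; if all were, it is f × m + (1 − f). With m = 50%:

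- f = 60%: from 30% to 30% + 40% = 70%.
- f = 90%: from 45% to 45% + 10% = 55%.

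Item 1c is the lower end of this range. It falls below the true rate whenever any alert with a missed follow-up was in fact mitigated.

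**The label.** Take a participant with 20 alerts (assumed) who answers every survey, does every spirometry and reports no mitigation. Then 1a = 20/20 = 100%, 1b = 20/20 = 100% and 1c = 0/20 = 0%, all three listed as compliance. This result owes nothing to missed follow-ups, since there are none. It arises only because the visible steps do not request the act that 1c counts.

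**A further ambiguity.** If the 30-minute notification were itself counted as an event-contingent prompt, each alert would add two to the denominator and 1c could not exceed 1/2 = 50%.

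**The case against.** The plan is silent on unanswered follow-ups, so the investigators may intend an answered-only denominator. Mitigation documented per alert is also a legitimate conservative measure for a feasibility study, and an answered-only proportion has its own bias if people who mitigate are likelier to answer. Item 1a already reports response. The three ratios are listed separately, with no composite and no decision rule. The rates used above are assumed.

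Much of this stands. It is why the per-alert ratio should be kept as a lower bound and why the impact is modest. It does not remove the point: the stated formula is the product of two quantities, and 1a pools prompts without giving response to the 30-minute survey separately.

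Three stronger readings are tempting, and the documents do not support them:

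- **That participants are never asked to change anything.** This holds only for the visible procedure text. The survey wording is in the Appendix and the follow-up flow is in Figure 4, neither of which is shown. The content of the set-up materials and live session is not given either. An instruction to mitigate could be in any of them.
- **That missed follow-ups make a fully compliant participant score zero.** Such a participant misses none. The zero comes from the label problem alone.
- **That 1c will be compared between subgroups or carried into the later study.** The planned comparison by participant characteristics concerns use and acceptance and does not name 1c. Specific Aims promises preliminary data for a powered study without naming a mitigation rate.

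**Conclusion.** The point holds in limited form. Read literally, 1c equals follow-up response times mitigation among answered follow-ups. It is a lower bound on per-alert mitigation and not a measure of compliance. With an assumed 50% mitigation rate, the shortfall is 5 percentage points at 90% response and 20 at 60%. This rests on reading the denominator as all alert-triggered prompts and on the 30-minute survey being the only source of the numerator. Taking 50% as the rate for all alerts also assumes that answering is unrelated to mitigating.

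The label problem is conditional on the unseen Appendix and Figure 4. The denominator problem remains even if they contain an instruction to mitigate. No stated decision depends on 1c, so the consequence is a feasibility result that is hard to interpret, not a wrong trial conclusion. It should still be corrected, because the formula is written down and would be followed.

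**What to change.** Replace 1c with two measures, each reported overall and by 4-hour period:

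1. **Compliance:** answered 30-minute surveys / alerts.
2. **Behavioural outcome, not labelled compliance:** alerts with any mitigation reported / alerts with an answered 30-minute survey.

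Keep alerts with mitigation reported / all alerts beside them, described as a lower bound. If the mitigation list has, or can be given, an option for nothing could be changed or not needed, also report measure 2 excluding those alerts. State that the 30-minute notification is not itself counted as an alert.

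The cost is a few lines of analysis text and possibly one response option; the data are already collected. The downside is that measure 2 rests on answered follow-ups and may be biased if people who mitigate are likelier to answer. Measure 1 and the lower bound are shown beside it for that reason.
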